STUDY TITLE: Cough Desensitization Therapy for Cough Hypersensitivity Syndrome

Clinicaltrials.gov identifier: NCT04256733

Document Date: 2/22/22

STUDY TITLE: Cough Desensitization Therapy for Cough Hypersensitivity Syndrome

Clinicaltrials.gov identifier: NCT04256733

Protocol:

Purpose: The purpose of this study is to investigate a modified behavioral treatment for chronic cough due to cough hypersensitivity syndrome (CHS). This type of CC is a non-productive cough that is due, in part, to over-expression of transient receptor potential vanilliod (TRPV) receptors in the airway epithelium⁵⁻⁹, which contributes to a dry cough elicited by typically non-tussive stimuli (e.g., cold air, smells) or by low doses of tussive stimuli (e.g., smoke). Currently available treatment options are limited to neuromodulator medications (e.g., gabapentin, amytriptiline)¹⁰⁻¹² and behavioral cough suppression therapy (BCST)¹³⁻¹⁶, neither of which is 100% effective. The primary component of BCST is teaching patients to suppress their cough in the presence of an urge-to-cough. Studies have confirmed a reduction in cough sensitivity (as tested with inhaled capsaicin) following 1-4 weeks of successful cough suppression^{13,17,18}. However, patients with severe CHS are not able to suppress their cough in the presence of uncontrollable environmental stimuli and, hence, do not respond well to the therapy. The purpose of this study is to determine the potential of treating CHS by implementing BCST while stimulating cough with progressive concentrations of inhaled diluted aerosolized capsaicin. The therapy is called cough desensitization therapy (CDT). The advantage of using capsaicin as a cough stimulant in the therapy is that it can be diluted to any concentration, which allows us to control the strength of the cough stimulant. Current research suggests BCST works by reducing cough sensitivity via neuroplasticity, as a result of suppressing cough when an urge-to-cough exists. The theoretical basis for CDT is exactly the same except that aerosolized capsaicin affords control over the cough stimulant, so that an urge-to-cough, that is strong enough to be felt but weak enough to suppress, can easily be produced. We hypothesize this treatment will result in a reduction in cough-reflex sensitivity, improvement in cough-related quality of life, and reduction in cough frequency.

Study design: Single-blind, sham-controlled randomized control trial **Study population:** Non-smoking males or females at least 18 years of age currently suffering from a non-productive cough that started at least 8 weeks ago, who meet the following inclusion/exclusion criteria:

- 1. have seen at least one physician for the cough;
- 2. have received medical treatment without success (i.e., refractory chronic cough);
- 3. have normal chest x-ray, pulmonary function testing, and laryngoscopy;
- 4. not diagnosed with a respiratory or pulmonary condition (e.g., asthma, COPD, emphysema, lung cancer, bronchitis);
- 5. not currently a smoker;
- 6. not taking any of the following medications within one month of enrollment: lisinopril/Prinivil/Zestril, captopril/Capoten, enalapril/Epaned/Asotec, ramipril/Altace, benazepril/Lotensin, fosinopril/Monopril, moexipril/Univasc, perindopril/Aceon, quinapril/Accupril, trandolapril/Mavik; and
- 7. willing to sign an informed consent form;

- 8. not pregnant and willing to take a pregnancy test before enrollment (if applicable).
- 9. Women who are of childbearing age, and have any potential of becoming pregnant, must agree to use contraception during the study.

Study duration: Six weeks per participant. 18 months to complete data collection.

Number participants planned: 20 (10 per group)

Study procedures: three phases

Phase I: Baseline Outcome Testing

Pulmonary function testing: Pulmonary function testing (PFT) will be completed using standard procedures. A minimum of two trials will be given to ensure reliability. Cough sensory testing will only proceed if PFT is normal.

Cough sensory testing: Standardized procedures that have been established and previously approved by the FDA (IND #69642 and #076866) will be used to determine participants' cough sensory threshold. All participants will complete spirometry testing before and after cough sensory testing. The following diluted capsaicin concentrations: .49, .98, 1.95, 3.9, 7.8, 15.6, 31.2, 62.5, 125, 250, 500, and 1000 μ M will be made prior to testing under the direct supervision of [name]. Participants will inhale single breaths of capsaicin aerosol through the DeVilbiss 646 nebulizer that is connected to a dosimeter (KoKo Digidoser). The single-dose method will be used during inhalation trials, with a delivery time of .6 second, which yields .002mL/inhalation. Table 1 shows the amounts of capsaicin per concentration that will be given per inhalation.. The initial concentration will be .49 μ M followed by subsequent doubling doses. We will determine the capsaicin concentration that causes two coughs (C2) and five coughs (C5) within 15 seconds of capsaicin inhalation. Capsaicin trials will be discontinued once the C5 level is determined, or the 1000 μ M dose is given, whichever comes first. We will also measure perceived urge-to-cough (UTC) following each inhalation of capsaicin on a scale from 0 (no UTC) to 10 (maximum UTC). This testing session will take approximately 30 minutes.

Table 1: Amount of capsaicin ingested per inhalation at each concentration.

Capsaicin ¹⁹	g Capsaicin Nebulized per inhalation
0.49	2.980e-10 (.000298 μg)
0.98	5.970e-10
1.95	1.193e-9
3.9	2.386e-9
7.8	4.772e-9
15.6	9.544e-9
31.2	1.908e-8
62.5	3.817e-8
125	7.635e-8
250	1.527e-7
500	3.054e-7
625	3.817e-7

750	4.581e-7
1000	6.108e-7

Cough frequency testing: Participants will be asked to wear a small digital mp3 audio recording device for 24 consecutive hours²⁰. The participant will simply clip the audio recorder to his/her belt or place the recorder in a pocket or fanny pack. A small microphone will be attached to the participant's shirt. The recordings will be analyzed by a software program to determine the exact frequency of coughs during the 24-hour period. The audio recordings will be deleted after they have been analyzed. The analysis is fully confidential and the recordings are deleted following analysis. [name], who conceptualized the assessment and created the computer program to analyze the recordings, named this method the Leicester Cough Monitor. The exact mp3 recorder (Sony ICD PX333 digital recorder) and microphone recommended by [name] have been purchased for this use.

Cough-related quality of life (QOL) testing: The Leicester Cough Questionnaire (LCQ)²¹ will be used to measure cough-related QOL.

Phase II: Treatment phase

Participants will attend treatment sessions 2 times per week for up to three weeks, with at least 3 days between each session. Each session will begin with PFT. Treatment will only proceed if PFT is normal. During treatment sessions participants will be exposed to aerosolized capsaicin in progressive doses while implementing cough suppression strategies. The first capsaicin dose will be one dose below each participant's C2 cough threshold dose. At least one minute will lapse between each capsaicin exposure and a sip of water will be allowed between each trial. The capsaicin concentration will increase when the participant is able to receive two exposures of the same dose without coughing. Each increase of capsaicin will be a doubling dose up to $500 \, \mu M$. Two concentrations between $500 \, \text{and} \, 1000 \, \mu M$ (i.e., $625 \, \text{and} \, 750 \, \mu M$) will be used to minimize the large increase between $500 \, \text{and} \, 1000 \, \mu M$. No more than 6 inhalations of capsaicin will be given in any single session and no more than 3 inhalations above $500 \, \mu M$ will be given in a single session. Each session will last $35-45 \, \text{minutes}$ (depending on scheduling constraints). We will measure the participant's number of coughs, urge-to-cough, and discomfort level (0-10) following each capsaicin inhalation.

Phase III: Post-Treatment Outcome Testing

Cough-sensory, cough-frequency, and cough-related QOL testing, as outlined in Phase I, will be completed at one week and three-weeks following the final treatment session. During cough-sensory and cough-frequency testing, participants will be instructed to NOT attempt to suppress their cough.

Statistical Analysis Plan:

The data will be analyzed with linear or generalized linear mixed models with a random subject effect to account for three repeated measurements (baseline, PT1, and PT2) on each participant, with fixed effects for the three time points and group (treatment, placebo) and their interaction, incorporated.

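### Does the instruction not to suppress cough apply at baseline as well as after treatment?

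*Combined protocol and SAP*

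**What the plan says.** The instruction appears once, in the paragraph headed Phase III: Post-Treatment Outcome Testing: "During cough-sensory and cough-frequency testing, participants will be instructed to NOT attempt to suppress their cough". The sentence before it says that "testing, as outlined in Phase I, will be completed at one week and three-weeks following the final treatment session".

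Phase I describes the same two tests. Cough sensory testing relies on "Standardized procedures that have been established and previously approved by the FDA", which are not reproduced. Cough frequency testing says that "Participants will be asked to wear a small digital mp3 audio recording device for 24 consecutive" hours, names the Leicester Cough Monitor and cites a source for it. Neither description mentions whether participants may hold back a cough.

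Baseline results are used twice. In Phase II, "The first capsaicin dose will be one dose below each participant's C2 cough threshold dose". In the Statistical Analysis Plan, baseline is one of three repeated measurements in a mixed model "with fixed effects for the three time points and group (treatment, placebo) and their interaction, incorporated".

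**The concern.** Voluntary suppression is the skill that the therapy uses, and the Phase III sentence shows that the sponsor thinks it can affect both tests. If participants were told not to suppress at one and three weeks after treatment but told nothing at baseline, the two occasions would differ in test condition as well as in time. Any coughs held back at baseline would lower the baseline count and raise the baseline thresholds, and the change from baseline would mix the effect of therapy with the effect of the instruction.

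The quantities at risk are the time effect and the change within each arm. These could be reported as results, because the Purpose section words the hypothesis as change: "We hypothesize this treatment will result in a reduction in cough-reflex sensitivity, improvement in cough-related quality of life, and reduction in cough frequency". The Statistical Analysis Plan does not say which model term tests it. The gap looks widest for the 24-hour recording, whose description does not appeal to approved standardized procedures.

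**Working it through.** The plan gives no figure on this point, so there is none to reproduce. The text is compared first, and the possible effect is then worked out under assumed inputs.

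**1. The text side by side**

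| Place | What it says about holding back coughs |
|---|---|
| Phase I, cough sensory testing | Nothing; relies on standardized procedures not shown |
| Phase I, cough frequency testing | Nothing; cites a source and a named method not shown |
| Phase II | Suppression strategies are used during treatment sessions |
| Phase III | Do not suppress, in both tests; no visit named |

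The text states no difference in conditions. It leaves one unstated.

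**2. Within-arm change in the 24-hour count**

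Let R be the true fall and s the share of coughs held back at baseline only. Both are assumed. The apparent fall is 1 − (1 − R)/(1 − s).

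| s | R = 30% | R = 50% |
|---|---|---|
| 0% | 30% | 50% |
| 5% | 1 − 0.70/0.95 = 26% | 1 − 0.50/0.95 = 47% |
| 10% | 1 − 0.70/0.90 = 22% | 1 − 0.50/0.90 = 44% |
| 20% | 1 − 0.70/0.80 = 12.5% | 1 − 0.50/0.80 = 37.5% |
| 30% | 1 − 0.70/0.70 = 0% | 1 − 0.50/0.70 = 29% |

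The error always runs toward understating improvement. The first row applies if the instruction is given at baseline, or if participants do not hold back.

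**3. Contrast between arms**

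The interaction at a post-treatment visit compares (post − baseline) in one arm with (post − baseline) in the other. Baseline precedes treatment, so randomization gives both arms the same expected baseline, whatever was said at the test. The two baseline terms cancel in expectation.

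On the ratio scale, take true falls of 30% (treatment) and 10% (sham), with s = 10%. The post/baseline ratios read 0.70/0.90 = 0.778 and 0.90/0.90 = 1.00. Their quotient is 0.778, and the true quotient is also 0.70/0.90 = 0.778. This holds for ratios, not for percentage falls: the falls read 22% and 0% in place of 30% and 10%.

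**4. Thresholds**

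If holding back raises a baseline threshold by k doublings, each change within arm drops by k. The difference between arms is (treatment change − k) − (sham change − k), so k drops out. This step-for-step identity fails near the top of the range, because testing stops at 1000 μM. A participant whose C5 would be 500 μM can rise by one step at most before the threshold goes unrecorded. The stop does not make expected baselines differ between arms, but the handling of unreached thresholds could matter a little.

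**5. Unequal holding back**

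If s varies between people, the contrast loses a little precision. Assume a within-person SD of 0.4 on the log scale and 10 per group, and compare the mean of the two post-treatment counts with baseline. The variance per person is 0.16 × 1.5 = 0.24, and the SE of the log ratio is √(2 × 0.24/10) = 0.219. If s is spread evenly from 0 to 40%, ln(1 − s) has variance 0.0761 − 0.0546 = 0.0215, and the SE becomes √(2 × 0.2615/10) = 0.229.

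**The case for a change.** The strongest case for a change has four parts.

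- **The cross-reference runs one way.** Phase III points back to Phase I, and nothing in Phase I takes up the instruction. That is true, and the gap in the text stands. But the sentence names the tests without naming a visit, directly after saying that they follow Phase I, so reading it as a rule for the tests themselves is natural.
- **Baseline participants may not be untrained.** Eligibility does not exclude earlier behavioral cough therapy, so some could hold back. This also stands. Against a large effect, the Purpose section describes suppression as something therapy teaches and says that severe patients fail at it when triggers are beyond their control. Eligibility does not require severe disease, so this argues for a small effect and does not prove a zero one.
- **Within-arm changes may be reported as the finding.** They may, but that would come from the plan not naming its test term, which is a separate matter. The trial is randomized and sham-controlled and its model contains the interaction, so a comparison that does not depend on the baseline instruction is available.
- **Baseline C2 also sets the first treatment exposure.** This is the most substantial part. A shifted C2 would change what is delivered in Phase II, so step 3 protects the measurement of the contrast but not the treatment received. The randomized comparison would still describe the therapy as delivered. Nothing in the documents shows that C2 is shifted.

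The recording is also not clearly worse placed than the capsaicin test. Both rest on outside sources that cannot be seen here, and either may already contain the instruction.

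**Conclusion.** The concern does not call for a change. The plan is silent on one detail of baseline testing, and the natural way to fill it is to give the same instruction each time the same test is run. The instruction is written where it is most needed, after participants have been taught to suppress.

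If it were given only after treatment, the group contrast would gain no bias from the measurement, apart from possible handling of thresholds not reached by 1000 μM and the link from baseline C2 to the first exposure. Within-arm changes would probably be understated: for a true 30% fall, they would read between 30% (no coughs held back) and 0% (an assumed 30% held back at baseline only). The documents support no particular value in that range, including any above zero. The conclusion rests on randomization giving both arms the same expected baseline and on the time-by-group term being the comparison of interest.

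Baselines already recorded could not be altered by new wording. Whatever was said at each visit can be stated when results are reported.

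### The SAP names no treatment contrast, leaves baseline means free and assumes equal correlations, so a change-from-baseline reading can lose precision and, if the correlations are unequal, exceed its nominal error rate

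*Combined protocol and SAP*

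**What the plan says.** The Study design section describes a "Single-blind, sham-controlled randomized control trial" with 10 participants per group. Phase III places the two post-treatment assessments (PT1 and PT2): testing "will be completed at one week and three-weeks following the final treatment session". Treatment lies between baseline and PT1: "Participants will attend treatment sessions 2 times per week for up to three weeks".

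The Statistical Analysis Plan is a single sentence. It specifies "linear or generalized linear mixed models with a random subject effect to account for three repeated measurements (baseline, PT1, and PT2) on each participant". The mean structure of these models is then described only as "with fixed effects for the three time points and group (treatment, placebo) and their interaction, incorporated". Baseline is therefore a response, not a covariate, and nothing makes the two arms share a baseline mean. No contrast, visit, alpha or correlation is given. The hypothesis under Purpose covers cough-reflex sensitivity, quality of life and cough frequency, and attaches no time point to any of them.

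**The concern.** Three levels of time by two groups with an interaction give six free cell means. With complete data, the interaction contrast at a visit is then the between-arm difference in mean change from baseline. That contrast spends information on estimating a baseline difference whose expected value is zero by randomisation. With 10 per arm this can matter.

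The sentence also allows several tests of the same effect: the 2-df interaction, change at PT1, change at PT2, change of their average, or a group difference at a post-treatment visit. They differ in power, and the choice stays open until the data are seen.

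Finally, reading the random subject effect as a random intercept, a linear model gives every pair of visits the same correlation. PT1 and PT2 are two weeks apart with no treatment between them, whereas up to three weeks of treatment separate baseline from PT1. A higher PT1-PT2 correlation is plausible, and the model's standard errors for change would then be too small.

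**Working it through.** **Inputs.** From the documents: n = 10 per arm, three visits, a random subject effect, free group-by-time means. Assumed, because the documents do not give them: linear model, SD 1 at every visit, two-sided 0.05, complete data, a sustained effect of 1 SD, and the correlations shown. The plan gives no power calculation to reproduce.

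Let a be the baseline-to-post correlation and b the PT1-PT2 correlation. Variances below are factors multiplied by 2/n = 0.2. Power is from the noncentral t with the degrees of freedom stated.

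**Step 1. Does the random-intercept model hold 5%?** Its residual variance estimates 1 minus the mean of the three correlations, 1 − (2a+b)/3. It therefore takes the variance factor of PT-average change as 1.5 × [1 − (2a+b)/3]. The true factor is (1+b)/2 + 1 − 2a. For one-visit change the model uses 2 × [1 − (2a+b)/3], and the true factor is 2(1−a).

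| a / b | PT average: model, true, ratio | One visit: model, true, ratio |
|---|---|---|
| 0.3 / 0.7 | 0.85, 1.25, 1.47 | 1.13, 1.40, 1.24 |
| 0.5 / 0.8 | 0.60, 0.90, 1.50 | 0.80, 1.00, 1.25 |
| 0.7 / 0.9 | 0.35, 0.55, 1.57 | 0.47, 0.60, 1.29 |

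The variance is understated in every row. In simulation under no effect, with 36 df, the PT-average change test rejected about 10 to 12% and the one-visit change tests about 8%. When all correlations are equal, the tests hold 5%.

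**Step 2. Power using tests that hold 5%.** Compare a two-sample t-test on each participant's PT-average change (18 df) with analysis of covariance of the PT average on baseline (17 df). The covariance-adjusted factor is [(1+b)/2 − a²] × (1 + 1/16), the last term being the cost of estimating the slope at N = 20.

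| a / b | Change: variance, power | Baseline as covariate: variance, power |
|---|---|---|
| 0.3 / 0.7 | 1.25 × 0.2 = 0.250, 47% | 0.76 × 1.0625 × 0.2 = 0.162, 65% |
| 0.5 / 0.8 | 0.90 × 0.2 = 0.180, 61% | 0.65 × 1.0625 × 0.2 = 0.138, 72% |
| 0.7 / 0.9 | 0.55 × 0.2 = 0.110, 81% | 0.46 × 1.0625 × 0.2 = 0.098, 85% |

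For one named visit only a matters. Factors 2(1−a) against (1−a²) × 1.0625 give 43 v 57%, 56 v 66% and 78 v 82% at a = 0.3, 0.5 and 0.7.

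**Step 3. Where the gain stops under equal correlations (a = b = r).** The SAP's change contrast now validly uses 36 df (critical value 2.028), and the covariate model 17 df (2.110). The squared ratio of critical values times the slope cost is (2.110/2.028)² × 1.0625 = 1.15. Covariate and change intervals have equal width when:
- one visit: 1.15 × (1+r)/2 = 1, so r ≈ 0.74;
- PT average: 1.15 × (1+2r)/3 = 1, so r ≈ 0.80.

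At r = 0.3, 0.5, 0.7 and 0.8 the width ratios (covariate over change) are 0.86, 0.93, 0.99 and 1.02 for one visit, and 0.78, 0.88, 0.96 and 1.00 for the average.

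**Step 4. Does the choice of contrast matter?** For a sustained effect the interaction has noncentrality 5 × (2/3)/(1−r) on F(2,36). Power at r = 0.3, 0.5, 0.7 and 0.8 under equal correlations:
- 2-df interaction: 45, 59, 82, 95%
- SAP change, PT average: 56.5, 71, 90, 98%
- SAP change, one visit: 45, 59, 80, 93%
- unadjusted group difference at one post visit (18 df): 56% at every r
- PT average with baseline as covariate: 78, 82, 93, 98%

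**The case against.** Group, time and interaction in a mixed model is a standard and valid analysis of a randomised trial. A reader might infer that free baseline means bias the result. They do not: the change contrast is unbiased, and its cost is precision only.

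A reader might also infer that the 2-df interaction is the weakest test on offer. Step 4 does not support that. It is weaker than the PT-average contrast, but equal to or slightly stronger than one-visit change. Nor is naming a 1-df contrast a gain in itself: at r = 0.7, moving from the interaction to one-visit change takes power from 82 to 80%. For the PT average at r = 0.6, naming the contrast takes power from 70 to 80%, and adding the covariate takes it to 87%, so both contribute.

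The correlations, SD, alpha and effect size are all assumed. If correlations are equal and high, the SAP's change contrast loses nothing to the covariate model. The raised error rate likewise needs unequal correlations, which the visit timing makes plausible but the documents do not establish.

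The scope is narrow as well. The linear-model figures fit the Leicester Cough Questionnaire, which "will be used to measure cough-related QOL". They do not carry over to the recordings used "to determine the exact frequency of coughs during the 24-hour period" if a generalized model is chosen, nor to C2/C5 thresholds capped at 1000 μM. All these limits stand. What remains is that the contrast is unnamed, that baseline is already collected, and that using it well needs only a wording change.

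**Conclusion.** The point holds as a should-fix item, with medium confidence. The text shows directly that no contrast is named and that the arms may differ at baseline.

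Under the assumptions in the working, adjusting for baseline adds 18 points of power for the PT average at correlations 0.3/0.7 (47 to 65%), 11 at 0.5/0.8 (61 to 72%) and 4 at 0.7/0.9 (81 to 85%). With equal correlations, the covariate interval is narrower only below r of about 0.74 for one visit or 0.80 for the average.

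The possible inflation of the error rate, to about 10 to 12% for PT-average change and about 8% for one-visit change, is more serious than the lost precision, but it is conditional. The documents do not support saying that this trial's error rate is doubled, or that the analysis is invalid. They support saying that the plan has no protection if PT1 and PT2 correlate more closely with each other than with baseline.

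**What to change.** For each outcome analysed with a linear model, prespecify one 1-df contrast: the PT1-PT2 average if a sustained effect is the target, or one named visit if waning is expected. Estimate it with baseline as covariate; for the average, use analysis of covariance of each participant's PT mean. An equivalent option is the three-visit model with a common baseline mean, an unstructured covariance and a small-sample correction. With complete data its maximum-likelihood estimate equals the covariate-adjusted one. Use the common-mean model with a single random subject effect only if equal correlations can be defended. Report both visit-specific differences with intervals. For any outcome under a generalized model, state the baseline adjustment on that model's own scale.

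The cost is SAP wording; no visit, procedure or participant is added. The statistical costs are fewer error degrees of freedom (17 against 36) and no gain at high correlation. Averaging also loses power if the effect wanes. At r = 0.5 (equal correlations) with a 1-SD effect at PT1 gone by PT2, the averaged effect is 0.5 SD with variance 0.5 × 1.0625 × 0.2 = 0.106. Power for the covariate-adjusted average is then about 30%, against 66% for covariate-adjusted PT1 alone and 59% for the interaction. The choice between average and single visit should therefore be argued in the SAP before unblinding.
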